17.2.3. ANALYSIS OF SECONDARY EFFICACY VARIABLES

All secondary efficacy analysis will be performed on the FAS (see Section 8).

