**Statistical Methods:**

The default summary statistics for continuous variables includes number of contributing observations (n), mean, standard deviation (SD), median, minimum, and maximum.

For categorical variables, the number and percentage (the percentage of subjects in each category relative to the total number of subjects in the relevant analysis population or relative to the total number of subjects in the relevant analysis population, with assessments available [where appropriate]) in each category will be the default summary presentation.

For primary and secondary continuous endpoints, change from Baseline will be evaluated where possible. Actual and change in data from baseline will be summarized descriptively for each treatment.

Frequency and percentages for each response Yes/No will be presented separately by visit. A shift table of change from Baseline to EOS will be displayed for each score.

[figure not shown]
For safety and tolerability, AEs, SAEs, vital signs, physical examinations, and laboratory assessments at specific time points will be evaluated. All safety data will be summarized descriptively. Number and percentage of AEs will be presented for each treatment by preferred term and system organ class of the current Medical Dictionary for Regulatory Authorities (MedDRA) dictionary. Individual listings of all SAEs and AEs leading to discontinuation from the study drug will be summarized using the current MedDRA dictionary. Similar analyses will be performed for potential significance and clinical importance of AEs.

Summaries and listings of data for vital signs, hematology, biochemistry, and urinalysis laboratory tests will be presented. Appropriate descriptive statistics will be summarized for the observed value at each scheduled assessment and for the corresponding change from Baseline. Baseline will be the last assessment before ANB019 dosing.

The PK of ANB019 will be evaluated by assessment of drug concentrations in serum. These drug concentrations will be listed and summarized for each sampling time point using appropriate descriptive statistics. The PK parameters will be summarized using appropriate descriptive statistics. Attainment of steady state will be graphically evaluated over the sampling period for the IV/SC treatment regimen.

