Concomitant medication	X o	X	X	X	X	X	X	X	X	X	X	X	X	X	X	X	X	X

Abbreviations: ADA = anti-drug antibody; AE = adverse event; BSA = body surface area; CGI = Clinical Global Impression; D = day; DLQI = Dermatology Life Quality Index; ECG = electrocardiogram; EOS = end of study; ET = early termination, FSH = follicle stimulating hormone; ICF = Informed consent form; PASI = Psoriasis Area Severity Index; JDA = Japanese Dermatology Association; PK = pharmacokinetics; QoL = Quality of Life; SAE = serious adverse event; TB = tuberculosis; W = week; WOCBP = Woman of childbearing potential.

- a. At Days 36, 50, 64, and 78, subjects will be contacted by phone for safety follow-up to assess for AEs and concomitant medications.
- b. In case of early discontinuation, the subject will be encouraged to return to the study center for the ET/EOS visit (Week 24/Day 169).
- c. Height to be measured at Screening only.
- d. Refer to Section 8.1 for details and instructions regarding CGI, JDA, PASI, total BSA as measured by modified JDA, GPPPGA, and QoL questionnaire (DLQI). The QoL questionnaire should be the first assessment completed by the subject before all other assessments at the study center except at the screening visit. At the screening visit, the ICF should be signed prior to QoL questionnaire and other study related assessments.
- e. Refer to Section 8.2.1 for details regarding complete physical examination. A complete physical examination will include assessments of general appearance; skin; head/neck; pulmonary, cardiovascular, gastrointestinal, external genitourinary, lymphatic, and musculoskeletal system; extremities; eyes (inspection and vision control); nose; throat; and neurologic status.
- f. Refer to Section 8.2.5 for details and instructions regarding ECG. In addition to the time points specified in SoA, ECGs may be performed at any time during the study if in the opinion of the Investigator it is clinically warranted.
- g. Vital signs assessment includes body temperature, pulse rate, blood pressure, and respiratory rate. Refer to Section 8.2.4 for details and instructions.
- h. Refer to Appendix 3 for details and instructions regarding clinical laboratory parameters and refer to Appendix 6 for the WOCBP definition.
- i. Bidirectional posteroanterior view and lateral view chest x-ray or as indicated by local treatment guidelines or practice will be performed at Screening. A chest x-ray is not required if performed within 6 months of Screening.

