### **6.5.1 Rescue Medicine**

Rescue medication will be directed by the Investigator as needed. Rescue medication in the form of topical corticosteroids (eg, betamethasone valerate ointment and cream, mometasone furoate ointment and cream) can be used during the study for a period of up to 1 week on a daily basis on affected areas to provide symptomatic relief. The introduction of any rescue medication must be communicated and discussed with the Medical Monitor. Rescue medication will be provided by the site and reimbursed by the Sponsor.

The use of rescue medications should be delayed, if possible, for at least 1 month following the administration of study treatment. Rescue medication may be used at the Investigator's discretion only if medically indicated for the wellbeing of the subject. The date and time of rescue medication administration as well as the name and dosage regimen of the rescue medication must be recorded.

The addition of any systemic psoriasis medication that is likely to impact psoriasis signs and symptoms (eg, cyclosporine, methotrexate, and retinoid) will require the subject to be withdrawn from the study.

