**Table 3 Analysis Sets**

Full Analysis Set (FAS)	The FAS analysis set will include all subjects, regardless of whether or not the treatment was received. Subjects will be analyzed according to treatment received.
Safety Analysis Set	The Safety Analysis Set will include all enrolled subjects who receive at least 1 dose of ANB019. The Safety Analysis Set will be used for all safety analyses. Subjects will be analyzed according to treatment received.
Per Protocol Analysis Set (PPS)	The Per Protocol analysis set will include all subjects in the FAS analysis set who do not have major protocol violations that would affect the evaluation of the primary efficacy endpoint.
PK Analysis Set	The PK analysis set will include all subjects in the Safety Analysis Set who have at least 1 quantifiable PK sample available and who do not have events or deviations with the potential to affect PK concentrations. The PK analysis set will be used for all PK analyses.

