3.3. EXPLORATORY ENDPOINTS

- Skin biopsy biomarkers (including but not limited to IL-17, IL-23, IL-8, dendritic cells, epidermal thickness, and leukocytes infiltration)
- Changes in serum cytokines as compared to Baseline at Weeks 1, 4, 8, 12, 16, and 24
- Photographic documentation of lesions
- Optional genetic testing (DNA and mRNA)

4. Hypothesis

No formal hypothesis testing will be performed.

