5.2. SAMPLE SIZE

The sample size is not based on statistical power considerations. Approximately 10 subjects will be enrolled at 8 study centers for study treatment.

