17.2.2. MISSING DATA METHODS FOR SECONDARY EFFICACY VARIABLE

If GPPPGA score is missing for a subject, for any reason, the score will not be imputed. Missing values for DLQI will be replaced using Last Observation Carried Forward (LOCF) for summarization of the results. All other missing values for secondary efficacy assessments will remain missing and not be imputed for any summary calculations.

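### The plan has no rule for efficacy values recorded after a subject starts a new systemic psoriasis drug, so Week 24/EOS summaries may count them as ANB019 results

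*SAP*

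**What the plan says.** **Conduct.** Protocol 6.5.1 says that adding a systemic psoriasis drug such as cyclosporine, methotrexate or a retinoid "will require the subject to be withdrawn from the study". Section 7.2 requires a withdrawn subject to attend an ET visit. Footnote b of the Schedule of Activities says that after early discontinuation "the subject will be encouraged to return to the study center for the ET/EOS visit (Week 24/Day 169)". CGI, modified JDA, GPPPGA, PASI and DLQI are all scheduled in that column.

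**Analysis.**
- SAP 17.2.3: "All secondary efficacy analysis will be performed on the FAS". The FAS carries no condition on other drugs: "The FAS analysis set will include all subjects, regardless of whether or not the treatment was received" (protocol Table 3; SAP Table A agrees).
- SAP Table B has a single analysis visit for Day 169, Week 24, EOS and ET.
- SAP 8.3 summarises by nominal visit. It keeps unscheduled values out of by-visit summaries but lets them feed the EOS, end-of-treatment and carried-forward values.
- SAP 17.2.2: "Missing values for DLQI will be replaced using Last Observation Carried Forward (LOCF) for summarization of the results". Other secondary variables stay missing when not observed.
- Protocol synopsis, Statistical Methods: "A shift table of change from Baseline to EOS will be displayed for each score". SAP section 17 does not list this table for efficacy scores, but SAP 5.4 declares no change from the protocol's analysis.
- SAP 14 only lists and summarises concomitant and rescue medication.

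**The concern.** Withdrawal governs conduct; it does not say what to do with data. The missing-data rules in SAP 17.1.2 and 17.2.2 apply only when a value is absent. A score observed while the subject takes cyclosporine is not absent, so under the nominal-visit and FAS rules it is summarised like any other.

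A subject who needs another systemic drug is, for the purpose of this study, a failure on ANB019. If the new drug works before the score is taken, that failure can appear as GPPPGA 0 or 1 at Week 24, as a favourable CGI category in the Week 24 display, as a favourable shift to EOS, or as an improved DLQI. SAP 17.2.1.7 reads the DLQI change as the effect of ANB019. With a single arm there is no comparator in which the same thing could happen and offset it.

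**Working it through.** **Inputs.** No stated figure bears on this point, so there is none to reproduce. SAP 5.2 says "The sample size is not based on statistical power considerations. Approximately 10 subjects will be enrolled at 8 study centers for study treatment", and SAP section 4 says "No formal hypothesis testing will be performed". The documents do not say how many subjects may start a systemic drug, so the sizes below are illustrations under stated assumptions.

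**Step 1. Is there a rule anywhere?** Neither document censors such a value, sets it to missing or counts it as failure. The per-protocol set is defined, but no efficacy analysis is assigned to it. SAP 17.1.4 plans no sensitivity analysis of the primary variable. SAP 18.3 does drop data from an affected period, but only for PK.

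**Step 2. By which routes can an affected value enter?**

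| Route | Condition | What it reaches |
|---|---|---|
| ET visit | Held after the first intake, including a return at Day 169 under footnote b | Week 24/EOS summaries, EOS shift tables |
| Unscheduled value | Taken on the new drug | EOS value, DLQI carry-forward |
| Scheduled visits | Subject kept in the study under the discretion in protocol 7.2 | Any later visit, including Week 16 response |

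**Step 3. Effect on a proportion.** SAP 17.2.1.4 divides by all enrolled subjects, about 10. If k affected subjects are all recorded as GPPPGA 0 or 1, the largest shift is 100 × k/10: 10.0 points for k = 1 and 20.0 for k = 2. Suppose 5 of 10 are recorded as 0 or 1 (50%, exact 95% CI 18.7 to 81.3). Counting affected subjects as not achieving it gives:
- k = 1: 4/10 = 40% (12.2 to 73.8)
- k = 2: 3/10 = 30% (6.7 to 65.2)

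**Step 4. Effect on mean DLQI change.** The shift is k × d/10, where d is the assumed gain from the other drug. For k = 1, d = 5, 10, 20 or 30 gives 0.5, 1.0, 2.0 or 3.0 points. The scale runs from 0 to 30, so 3.0 is the ceiling for one subject.

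**Step 5. How likely is at least one case?** With per-subject probability p (assumed) of starting a systemic drug, the chance is 1 − (1 − p)^10: 40% for p = 5%, 65% for 10% and 89% for 20%. This counts starters. Only those with a score taken on the new drug are affected, so these are upper limits on the chance of an affected result.

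**Step 6. DLQI carry-forward.** A last value placed by date at Day 57 would fill Days 71, 85, 113, 141 and 169, five visits; at Day 85 it would fill three. If the same value is labelled Week 24, as Table B suggests for an ET visit, no later visit remains to fill. The SAP does not say how an early ET visit is placed.

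**The case against.** The strongest reply is protocol 6.7. It treats the ET visit as an alternative to Day 169 and leaves treatment to the Investigator's judgment after that visit. Appendix 5 gives a similar order: if a prohibited treatment is essential, the subject tells the study team and is withdrawn. On that reading, ET scores are taken before the other drug starts and nothing is affected. This stands as the implied sequence. It does not close the gap, because 6.5.1 makes the addition of the drug the trigger, footnote b attaches Week 24/Day 169 to the visit, and no analysis rule applies if the order is reversed.

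Four stronger readings are tempting, and the documents do not support them:
- **That withdrawn subjects are normally assessed after weeks on another drug.** This takes the column label in footnote b as a date for every early withdrawal. Section 6.7 points the other way.
- **That the Week 16 primary result is generally affected.** Week 4 non-responders remain non-responders at Week 16 under SAP 17.1.2, and later withdrawals should have no Week 16 visit. Only a subject kept in the study would be affected.
- **That an affected DLQI value is routinely carried through several visits.** This needs a last observation taken on the new drug and placed by date before Week 24. It cannot be combined with an ET visit labelled Week 24.
- **That the bias always favours ANB019.** A score taken in a flare, before the new drug works, lowers the late results.

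It is also fair to say that using all observed data regardless of other drugs is a legitimate strategy, that the study is exploratory and descriptive, and that medications and individual scores are listed, so a reader could identify an affected subject. But the SAP does not state that strategy, and a listing does not correct a summary table.

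**Conclusion.** The gap is real and should be closed. It concerns mainly the Week 24/EOS secondary summaries, which fall 12 weeks after the last dose (Day 85 to Day 169 is 84 days). The Week 16 primary response is exposed only through a subject who starts a systemic drug and is not withdrawn.

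One affected subject moves a proportion by up to 10 points and mean DLQI change by at most 3.0 points, taking n = 10. The size rests on two assumptions: that at least one subject starts a new systemic drug, and that a score is then taken on it. The direction also depends on when that score is taken; a response to the other drug would favour ANB019. The documents fix none of these.

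**What to change.** Add to both SAP 17.1.2 (primary) and SAP 17.2.2 (secondary):

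> Efficacy values dated after the first intake, after Day 1, of a newly started or restarted systemic psoriasis therapy (protocol 6.5.1 and Appendix 5; tapering washout of prior therapy excluded) are listed but not included in the main summaries. For CGI response and GPPPGA 0/1 the subject counts as a non-responder from that date. Such values are not used as EOS values or carried forward for DLQI. Results using all observed data are shown as a supportive summary.

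The qualifiers on Day 1 and washout are needed because the protocol allows tapering of earlier systemic therapy to overlap the start of study drug. Without them, the rule could remove data from subjects treated before entry.

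State in SAP 8.3 or 8.4 how an early ET visit maps to an analysis visit.

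The sponsor must also reconcile footnote b with protocol 6.7 on the timing of the ET visit, and 6.5.1, 7.2 and Appendix 5 on when a prohibited drug leads to withdrawal. Which reading is intended is for the sponsor to decide.

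**Cost.** A few lines of SAP text and one date comparison. Protocol 6.5 already collects medication start and end dates, so no new data are needed. The downside is slightly lower late response rates and fewer observed values at Week 24/EOS.

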17.3. EXPLORATORY EFFICACY

17.3.1. PHOTOGRAPHIC DOCUMENTATION OF LESIONS

Photography of the lesions will be performed for documentation purposes only. This will not be shared with Biostatistics for analysis.

18. PHARMACOKINETICS

Derivation of serum PK parameters following ANB019 treatment will be the responsibility of the clinical pharmacokineticist at **Example**. The PK summaries, summary figures, and data listings as well as the statistical analysis of the PK variables will be the responsibility of the study biostatistician at **Example**. Some minor modifications may be necessary to the planned design of tables, figures, and listings to accommodate data collected during the actual study conduct.

18.1. VARIABLES & DERIVATIONS

18.1.1. SERUM CONCENTRATION DATA

A subject listing of all concentration-time data following IV and SC injections will be presented by subject and scheduled sample collection time. Concentration data of ANB019 will be summarized by route/day and nominal time point using N (sample size), n (available data), arithmetic mean, standard deviation (SD), coefficient of variation (CV), minimum, median, maximum, and geometric mean using the respective PKAS. Concentrations that are below the limit of quantitation (BLQ) will be treated as zero for the computation of descriptive statistics. Graphs for ANB019 mean concentration-time data following IV administration will be presented in linear and semi-logarithmic scale. Trough concentrations following and including Day 29 will be presented as scatter plots. By-subject plots will be presented in linear and semi-logarithmic scale.

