### 9.4.7.2 Pharmacokinetic Concentration Data Analysis

A subject listing of all concentration-time data following study drug administration will be presented by subject and scheduled sample collection time.

Concentration data of ANB019 will be summarized by route/day and nominal time point using the number of observations (n), arithmetic mean, SD, coefficient of variation (CV), minimum, median, maximum, and geometric mean.

Graphs for mean concentration-time data following IV administration will be presented. Individual subject plots will also be presented. Other presentations of data may be added at the discretion of the PK scientist, as appropriate, and will be described in detail in the SAP.

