5. STUDY DESIGN

5.1. GENERAL DESCRIPTION

This is an open-label, single arm, multiple dose study to assess the clinical efficacy, as well as the safety, tolerability, and PK of multiple doses of ANB019 in subjects with GPP.

The screening period will be up to 42 days (6 weeks) prior to administration of study drug on Day 1. Written informed consent will be obtained from each subject prior to initiating any study related procedures. All screening procedures will be conducted in accordance with the Schedule of Activities (see Section 1.3 in the protocol). On Day 1, subjects who meet the entry criteria will receive a 750 mg IV dose of ANB019 in an open-label manner, followed by 3 doses of 100 mg SC administered on Days 29, 57, and 85.

Subjects will leave the study center after completion of the 5 hours postdose assessments following IV administration and the 3 hours postdose assessments after the first and second SC injections and with the investigator's approval. Subjects with any ongoing AEs or SAEs at the time of scheduled discharge from the study center should remain at the study center until the Investigator has determined that these events have resolved or are deemed as not clinically significant.

After completing Day 1 assessments, the subjects will return to the study center for follow-up visits on Days 3, 8, weekly from Day 8 to Day 29, every other week up to Day 85, then monthly for 12 weeks to monitor changes in disease activity, safety, and tolerability. In addition, subjects will be contacted via phone by study staff to assess for safety (e.g., AEs and changes in concomitant medications) on Days 36, 50, 64, and 78.

Subjects who are non-responders at Week 4 will be early terminated 4 weeks after the 750 mg IV dose administration. A non-responder is defined as a subject who experiences:

- "No change" on Clinical Global Impression (CGI): 0 points change in JDA total score and not meeting "other criteria" for minimally improved.
- "Worsened" based on CGI: ≥1-point increase in JDA total score.

[figure not shown]
Disease activity (response to study treatment) will be evaluated using the CGI scale according to the mJDA severity index, change in total area of erythema with pustules, erythema, and edema as measured by modified JDA index, systemic manifestations and laboratory findings as per modified JDA severity index, GPPPGA scale, and PASI score (if PP is present). Quality of life (QoL) will be assessed using the DLQI.

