18.1.2. PHARMACOKINETIC PARAMETERS

Subjects with partial data will be evaluated on a case-by-case basis to determine if sufficient data are available for reliable estimation of PK parameters.

For PK parameter calculations following IV dose:

- Concentrations that are BLQ or missing at pre-dose or the beginning of the curve will be set to zero.
- Any other BLQ concentrations will be assigned a value of zero if they precede quantifiable samples in the initial portion of the profile.
- A BLQ value that occurs between quantifiable data points, especially prior to C_{max}, will be evaluated to determine if an assigned concentration of zero makes sense, or if exclusion of the data is warranted.
- Following C_{max}, BLQ values embedded between two quantifiable data points will be treated as missing when calculating PK parameters.
- If a BLQ value occurs at the end of the collection interval (after the last quantifiable concentration), it will be set to zero.
- If consecutive BLQ concentrations are followed by quantifiable concentrations in the terminal portion of the concentration curve, these quantified values will be excluded from the PK analysis by setting them to missing, unless otherwise warranted by the concentration-time profile.

The following PK parameters will be calculated following IV administration of ANB019 by noncompartmental methods, using actual elapsed time from dosing.

C _{max}	Maximum observed concentration, obtained directly from the observed concentration versus time data.	
t _{max}	Time of maximum observed concentration, obtained directly from the observed concentration versus time data.	
t _{1/2}	Apparent terminal half-life (h), determined as $(\ln 2/\lambda z)$	
CL	Systemic clearance (L/h) calculated as dose/AUC _(0-last)	
Vz	Volume of distribution (L) during terminal phase, estimated by dividing the systemic clearance by λz .	
λz	Apparent terminal rate constant (1/h), determined by linear regression of the terminal points of the log-linear concentration-time curve.	
AUC(0-last)	Area under the concentration-time curve (AUC) from time zero (pre-dose) to time of last quantifiable concentration, calculated by linear up/log down trapezoidal summation.	
AUCoverall	Area under the concentration-time curve (AUC) from time zero (pre-dose) on Day 1 (IV dose) to time of last quantifiable concentration following Day 87 SC dose	
Note: The dat	Note: The data from Day 1 to Day 29 pre-dose will be used to calculate the first 7 parameters.	

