18.2. MISSING DATA METHODS

Missing pharmacokinetic data will not be imputed. Further discussion of treatment of missing data is dealt in Section 18.1.2

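### SAP 18.1.1 sets BLQ concentrations to zero and also asks for geometric means, so the geometric mean is 0 or not computable wherever a value is BLQ

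*SAP*

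**What the plan says.** SAP Section 18.1.1 lists the statistics for the concentration tables, ending with "minimum, median, maximum, and geometric mean using the respective PKAS". The next sentence says that BLQ concentrations "will be treated as zero for the computation of descriptive statistics". Nothing there exempts the geometric mean.

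Other places that might have settled the matter do not:

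- **Protocol 9.4.7.2** asks for the same tables ("Concentration data of ANB019 will be summarized by route/day and nominal time point using the number of observations (n), arithmetic mean", with the geometric mean last in its list) and gives no BLQ rule.
- **SAP 18.1.2** has detailed BLQ rules, but they are introduced by "For PK parameter calculations following IV dose". They govern the non-compartmental parameters, not the concentration tables.
- **SAP 18.2** says "Missing pharmacokinetic data will not be imputed" and refers back to 18.1.2.
- **SAP 18.4** covers PK parameters, and **18.5** covers only the rounding of the geometric mean.
- **SAP 19.2.1** has a substitution rule for results outside the quantifiable range, but it applies to clinical laboratory tests.

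Membership of the PK analysis set needs only one quantifiable sample (SAP Section 8, Table A). A subject's BLQ samples at other visits therefore stay in the summaries.

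**The concern.** The two instructions in 18.1.1 cannot both be carried out to give a usable number at a time point where any subject is BLQ. The plan does not say what the programmer should do then, so the choice would be made after the data are in hand.

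One possible choice is worse than an empty cell. If log(0) is treated as missing and dropped, the geometric mean describes the quantifiable subjects while the arithmetic mean beside it still includes the zeros. The table would give no sign that the two rest on different subjects. Serum concentration is a secondary endpoint, so the rule should be fixed in advance even though the tables are descriptive.

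**Working it through.** The plan states no figure on this point to reproduce. The check has four steps.

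**1. What the written rule gives.** For values x₁…xₙ the geometric mean is (x₁·x₂·…·xₙ)^(1/n), or exp(mean of ln x). With one zero, the product form gives exactly 0. The log form needs ln 0 = −∞ and cannot be computed.

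**2. Where BLQ values may occur.** Protocol Table 2 schedules PK samples at Day 1 pre-dose and at Days 113, 141 and 169, among others. The pre-dose sample should be BLQ in essentially every subject. Dosing is 750 mg IV on Day 1, "followed by 3 doses of 100 mg SC administered on Days 29, 57, and 85", so Days 141 and 169 fall 56 and 84 days after the last dose. The text available to me gives no LLOQ and no human half-life. It gives a monkey half-life of 310 h after SC dosing (Protocol 2.2.1). Taking that purely as an assumption:

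| Visit | Hours after Day 85 | Half-lives | Share of last dose's contribution left |
|---|---|---|---|
| Day 113 | 28 × 24 = 672 | 672/310 = 2.17 | 22% |
| Day 141 | 56 × 24 = 1344 | 1344/310 = 4.34 | 5% |
| Day 169 | 84 × 24 = 2016 | 2016/310 = 6.50 | 1% |

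BLQ values are therefore most plausible at the last two visits. That does not show they will occur.

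On size: "Approximately 10 subjects will be enrolled at 8 study centers for study treatment". With n = 10 and an assumed per-sample BLQ probability p, the chance of at least one BLQ value at a visit is 1 − (1 − p)^10. This is 40%, 65%, 89% and 97% for p = 5%, 10%, 20% and 30%. It is lower if fewer than 10 subjects remain.

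**3. What dropping zeros would do (not in the SAP).** Assume lognormal concentrations with σ = √ln(1 + CV²), BLQ fraction f and a = Φ⁻¹(f). The geometric mean of the quantifiable values divided by the true one is exp(σ·φ(a)/(1 − f)). The term φ(a)/(1 − f) is 0.195, 0.497 and 0.798 for f = 10%, 30% and 50%.

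| CV (assumed) | σ | 10% BLQ | 30% BLQ | 50% BLQ |
|---|---|---|---|---|
| 30% | 0.294 | 1.06 | 1.16 | 1.26 |
| 50% | 0.472 | 1.10 | 1.26 | 1.46 |
| about 95% | 0.8 | 1.17 | 1.49 | 1.89 |

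**4. One invented table row.** Take LLOQ = 1, three of ten values BLQ, and the rest 1.2, 1.5, 2.0, 2.6, 3.1, 4.0 and 5.5.

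- Arithmetic mean with zeros: 19.9/10 = 1.99.
- Geometric mean with zeros kept: 0 or not computable.
- Geometric mean with zeros dropped (n = 7): 2.52. This exceeds the arithmetic mean, which cannot happen on one common set of values.
- Geometric mean with BLQ set to LLOQ/2: 1.55; with BLQ set to LLOQ: 1.91.

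LLOQ/2 is a convention, not a correction. Under the lognormal assumption of step 3 its ratio to the truth is exp(f·ln(q/2) + (1 − f)·σ·φ(a)/(1 − f)), with q = exp(σa), the LLOQ relative to the true geometric mean. At CV 50% this gives 0.95, 0.89 and 0.85 for 10%, 30% and 50% BLQ.

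**The case against.** The strongest reply is that the written rule misleads nobody. Followed literally, it prints 0 or a blank, which any reader would notice. The arithmetic mean, median, minimum and maximum in the same row can still be computed, and a minimum of 0 flags BLQ values. Individual concentrations appear in the listing and the by-subject plots, and troughs also in scatter plots. C_max and AUC after the IV dose have their own BLQ rules. No hypothesis is tested, and no efficacy or safety result uses this statistic. The one near-certain case, Day 1 pre-dose, is harmless. All of this stands, and it keeps the point minor.

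It also rules out stronger readings that a reader might infer:

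- **That the plan overstates late concentrations.** The documents do not support this. The overstatement needs a further step, dropping zeros, which the SAP never states and which departs from its own rule. Post-dose BLQ values may also turn out to be rare.
- **That fast clearance through anti-drug antibodies would be hidden.** Such a subject is visible in the listings and individual plots. The optional summary by antibody status in SAP 18.4 concerns PK parameters, not the concentration tables.

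The reply does not remove the conflict itself. An instruction that yields 0 or nothing for a requested statistic is still wrong, and no other section repairs it.

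**Conclusion.** Wrong as written, but minor. SAP 18.1.1 requests a statistic and sets a data rule that makes it 0 or not computable at any time point with a BLQ value. That much follows from the text and the definition of the geometric mean, with no assumption about the data.

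The overstatement factors, 1.06 to 1.89 across the range shown, are conditional on zeros being dropped, on lognormal concentrations, and on assumed CVs and BLQ shares. They show why the choice should not be left open; they do not predict this trial's results. The effect is confined to the descriptive PK concentration tables.

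**What to change.** Amend SAP 18.1.1 as follows:

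1. Limit the zero rule to the arithmetic statistics: mean, SD, CV, minimum, median and maximum.
2. State one rule for the geometric mean. Either of these would do: (a) it is not calculated when any value at that time point is BLQ; or (b) BLQ is set to a stated value such as LLOQ/2, and the geometric mean is not reported when more than half the values are BLQ.
3. Do not report the geometric mean for Day 1 pre-dose.
4. Show the number of BLQ values at each time point.

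Option (a) is simpler but leaves more blank cells. Option (b) fills them, but the arithmetic and geometric means in one row then treat the same samples differently, so a table footnote should say so. No rule for geometric CV is needed here, because 18.1.1 does not request it for concentrations.

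The cost is a sentence or two in the SAP and one extra row in the concentration table shell. No data collection or protocol change is needed.
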